7 DATA COLLECTION

Data will be collected in the form of observations and then entered upon leaving the facility within one hour of the observation. For the purpose of ensuring accurate data entry, the data collector will use the audio recording and the prescription, the copy of which will be kept with them.

A detailed checklist will be used to assess the adherence of the healthcare providers to standard guidelines. This checklist will include all aspects covered in section 6.1:

- ✓ History taking
- ✓ Examination
- ✓ Diagnosis
- ✓ Treatment/management

These areas encompass the guidelines of essential care for pneumonia. Here essential care refers to the questions providers must ask the caregiver and examinations provider must conduct to accomplish correct diagnosis.

7.1 Source Data Documentation

The checklist will be developed in the form of a structured Urdu questionnaire which will be pretested. It will then be transformed into a soft version using our online questionnaire development dashboard. The questionnaire will then be installed into tablets.

Data will be collected in tablets to avoid errors of skips and logic. It will have an essential component of not accepting incomplete forms which will ensure that complete data is being collected on site. This data will be sent to our headquarters from all over the country via online server. This will ensure rapid access to data and data confidentiality as it will only be accessed by our data manager located in the headquarters through a password restricted data dashboard.

Each data collector will be provided a tablet, its charging cable and a power-bank to ensure that the tablet is charged all the time. In case any technical error is faced in any of the tablets, he/she will inform the supervisor who will arrange an alternate tablet to enter data. Additionally, the data collector will also have extra hard copies of the questionnaires to enter data in case a technical error occurs in the tablet and if there is a delay in delivery of an alternate one. These hard copies will be sent to the project manager via courier on the same of completion of data collection to avoid delay in data entry. The data collector will also maintain a contact sheet which will include information on the location, date and time of the observation, name of the child and caregiver, phone number, observed health professional's name and level of health facility/care.

In order to ensure that data is provided timely, the data collector will be asserted on sending the entered data as soon as the form in the tablet is filled. Therefore, each tablet will have a network enabled sim with an internet connectivity which will ensure that the data is transferred timely. In case there is decreased network coverage, the data collector will send the form as soon as an area of strong connectivity is reached. Additionally, if he/she reaches a location which has Wi-Fi connectivity then it will be used to send the forms. In case a tablet gets lost as soon as the observation is made, then the data collector will inform the supervisor who will arrange an alternate tablet and will check whether all data has reached the server or not. In case partial data is obtained, then those cases will be identified and the data collector will be asked to fill another observation form (using the recordings and recall) in the replaced tablet and ensure that data has been obtained by the supervisor. Tablets will be password enabled such that no one can gain access into the data except for the data collector. Considering all data will be sent to the server immediately after collection and will not be saved within the tablets, therefore even on being lost no one will be able to access the data.

7.2 Case Report Forms

Electronic CRFs (eCRFs) will be used for improved data quality, avoidance of manual data entry errors and confidentiality etc. It will include the following key points:

- ✓ Protocol ID
- ✓ Site code
- ✓ Subject ID

- ✓ Respondent Initials
- ✓ Respondent demographics (age, gender, educational level)
- ✓ Age of the youngest child
- ✓ Phone number
- ✓ Alternate phone number
- ✓ Prescription picture
- ✓ GPS location
- ✓ Date of visit
- ✓ Place of visit (LHW/BHU/RHC/Private clinic/Public tertiary hospital)
- ✓ Name of the healthcare provider
- ✓ Data collector initials/ID
- ✓ Time spent in consultation
- ✓ Visit checklist (as indicated by section 6.1)
- ✓ Reason of withdrawal from the study

8 STATISTICS AND DATA ANALYSIS

8.1 SAMPLE SIZE CALCULATION

Considering this is a qualitative study therefore an approximate estimate of the sample will be provided. Event sampling will be employed whereby a pre-defined checklist of behaviours will be developed to record all occurrences. The sample size is based on point of theoretical saturation although we plan to conduct at least 32 observations from each of the four provinces and the federal capital (LHWS; 6, BHU Medical officer; 4, RHC medical officer; 4, private practitioner; 9, and public practitioner; 9). Thus a minimum of 160 observations will be conducted. Data will be collected over a period of six months.

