2.1.2 Secondary Objectives

To determine the differences in pneumonia case management observed across the provinces of Pakistan in both public and private sector.

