3 STUDY DESIGN

3.1 Methodology:

This will be a qualitative study which will be conducted through participant observations over a period of 13 months across randomly selected sites in four provinces of Pakistan in addition to the federal capital. The provinces are Baluchistan, Khyber Pakhtunkhwa (KPK), Punjab and Sindh.

After obtaining ethical clearance, an observation tool will be developed based on standard WHO guidelines and input from field experts. This tool will be pretested upon finalization. At the same time an advisory committee will also be formulated composed of expert paediatricians and public health professionals who will provide their input into the implementation protocol and the tool. Once the tool is finalized trainings will be conducted on the tool and then observations will be conducted.

3.2 Observation Sites:

Observations sites will be randomly selected from each of the four provinces and the capital through our specialized sampling software. Upon site selection, observations will be made across the following levels of healthcare: community level, first level care facility (FLCF) and practitioner level both in the public and private sector. The community level observations will include observation of the pneumonia case management by the LHWs. LHWs are the primary care givers at the community level who cover around 60% of Pakistan. Their basic duties include education, counselling and basic management of the common maternal and child ailments. Each LHW covers around 100-120 household and visits each household once a month. The observations will be made either at the health house of the LHW or she will be requested to visit the household of the disguised patient.

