8.2 PROPOSED ANALYSES

Behavioural coding will be employed to prepare the data for analysis. This means that a predetermined code will be given to each variable against each category of observations (History, examination, diagnosis and treatment). Each variable will be answered as "Y" meaning yes, the task was accomplished and "N" meaning no, the task was not accomplished (section 6.1). Additionally, the responses will be labelled as correct, partially correct and incorrect for history taking and examination. If on history taking, the healthcare provider asks questions on all variables, then the responses will be labelled as correct and if any one variable is missed then the response is indicated as partially correct and in case less than 50% of the variables are asked about, then the responses will be labelled as incorrect. The same labels will be specified for the examination. In case of diagnosis and treatment, the labels will be specified as correct and incorrect only as there is no partially correct diagnosis and treatment regimens. The overall frequencies and percentages of these responses will be calculated and cross tabulated across the provinces.

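### Section 8.1 rests the sample size on theoretical saturation, which a closed Y/N checklist reported as percentages cannot show; the plan needs a fixed, reconciled number with its expected precision

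*Combined protocol and SAP*

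**What the plan says.** Section 3.1 introduces the study so: "This will be a qualitative study which will be conducted through participant observations over a period of 13 months". Section 8.1 uses that label as its reason for giving no formal calculation: "Considering this is a qualitative study therefore an approximate estimate of the sample will be provided". It then names the basis: "The sample size is based on point of theoretical saturation although we plan to conduct at least 32 observations". That floor applies in five locations, the provinces and the capital. The quota within each location is "LHWS; 6, BHU Medical officer; 4, RHC medical officer; 4, private practitioner; 9, and public practitioner; 9", and the section concludes: "Thus a minimum of 160 observations will be conducted".

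The analysis in section 8.2 gives every variable a code set in advance, scores it Y or N, and labels history and examination as correct, partially correct or incorrect, and diagnosis and treatment as correct or incorrect. The output is stated so: "The overall frequencies and percentages of these responses will be calculated and cross tabulated across the provinces". The secondary objective (section 2.1.2) is comparative: "To determine the differences in pneumonia case management observed across the provinces of Pakistan in both public and private sector".

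No section defines saturation, names who would judge it or when, or plans a thematic analysis.

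**The concern.** The stated basis and the data do not match. Saturation is a property of open-ended material: one stops when new observations no longer produce new categories. The tool in Annex C has 12 history, 6 examination, 1 diagnosis and 1 management entries, 20 in all, fixed before the first visit. A further visit can add no category; it can only narrow a percentage. The size therefore has no valid stated basis, and the qualitative label is what excuses the lack of one.

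Two things are at stake. First, a reader told that size rests on saturation is not told how precise the percentages will be, although one objective is to compare provinces within each sector. Second, a floor without a ceiling, with saturation as the named basis, leaves it unclear when collection ends.

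**Working it through.** **1. The plan's own figure.** Quotas from section 8.1: 6 + 4 + 4 + 9 + 9 = 32 per location. Four provinces plus the capital make 5 locations: 32 × 5 = 160. The total reproduces, but only as addition of quotas. The documents give no confidence level, expected proportion, target precision, power or saturation criterion from which 32 or 160 could follow.

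**2. Could anything else in the design saturate?** Audio recordings serve to complete the checklist and validate the visit (sections 3.5 and 7). Annex C ends with one free-text line, but section 8.2 plans no analysis of it. Section 5.1 draws BHUs, RHCs and practitioners at random from lists. These are the features of a structured survey.

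**3. Precision with 160 visits.** Assumptions, none of them from the documents: 95% confidence, independent visits, p = 0.5. Half-width = 1.96 × √(0.25/n) = 0.98/√n. Half-width for a difference between two locations = 1.96 × √(2 × 0.25/n). Section 1.1 counts LHWs, BHUs and RHCs as public sector, so public providers per location are 6 + 4 + 4 + 9 = 23.

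| Group | n | Half-width (points) | Two-location difference (points) |
|---|---|---|---|
| All visits | 160 | 7.7 | – |
| One location | 32 | 17.3 | 24.5 |
| Public providers, one location | 23 | 20.4 | 28.9 |
| Private practitioners, one location | 9 | 32.7 | 46.2 |

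A proportion of 0.5 gives the widest interval for a given n. At p = 0.3 the figures are 7.1 overall and 15.9 per location; at p = 0.1, 4.6 and 10.4. The normal approximation is rough at n = 9, but the exact 95% interval for 4 of 9 is 13.7% to 78.8%, so the message is the same.

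As a further gauge, take 50% against 70% in two locations of 32, two-sided 5%. With the pooled standard error √(2 × 0.6 × 0.4/32) = 0.1225 and the unpooled one √((0.25 + 0.21)/32) = 0.1199, power = Φ((0.20 − 1.96 × 0.1225)/0.1199) = 0.37.

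**4. Clustering.** Section 4.1 has two data collectors per location, so 32/2 = 16 visits each, and lets one caregiver serve for the LHW, BHU and RHC where cases are few. For illustration, assume an intraclass correlation by data collector of 0.05 to 0.10. The design effect 1 + (16 − 1) × ICC is 1.75 to 2.50, and its square root is 1.32 to 1.58. The overall half-width becomes 7.75 × 1.32 = 10.2 to 7.75 × 1.58 = 12.2 points, or about 10 to 12. Per location, 17.3 becomes about 22.9 to 27.4.

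**5. The number itself is in conflict.** Section 5.1 selects five practitioners each from the public and private sector; section 8.1 says nine and nine. Read per province, section 5.1 gives 6 + 4 + 4 + 5 + 5 = 24 per location and 24 × 5 = 120 in total. Half-widths are then 0.98/√120 = 8.9 overall, 0.98/√24 = 20.0 per location, 0.98/√19 = 22.5 for public providers (6 + 4 + 4 + 5 = 19) and 0.98/√5 = 43.8 for private practitioners.

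**The case against.** The strongest answer is that the saturation sentence does no work. Collection is bounded by fixed quotas and six months (section 8.1) and by 160 caregivers, one per observation (section 4.1). The work-plan in section 3.6 puts data collection in months 4 to 9 and analysis from month 10. Section 4.1 adds a site only when the planned number cannot be reached, not because of what has been seen. This stands.

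It also disposes of a stronger reading. From *at least* and *minimum* a reader might infer that a province's sample could be extended in the light of its results, and that the percentages could be biased by such stopping. The documents provide for no look at results followed by more sampling. And if saturation cannot be observed on this checklist, it cannot act as a results-driven stop either. What remains is ambiguous wording that leaves a risk open.

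It can also be said that nothing is concealed, because section 8.1 prints the cell counts, and that section 8.2 plans cross-tabulation only, with no test or claim of power. This too stands. A reader might infer that the plan claims to detect provincial differences, but it makes no such claim. Even so, percentages from cells of 9 or 23 need intervals to be read properly, and section 8.2 plans none.

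**Conclusion.** The point holds as a mismatch between justification and design. Theoretical saturation is not a valid basis for the size of a closed-checklist survey, and no other basis is given. The arithmetic of 160 is sound, but the number is contradicted by section 5.1, and its end point is worded ambiguously. Biased stopping is not shown.

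With 160 visits, the survey describes the whole sample to about 7.7 points and a location to about 17.3. Differences between two locations carry about 24.5 points overall, 28.9 in the public sector and 46.2 in the private sector. These figures are the widest as regards the proportion (p = 0.5) but best case as regards dependence: they assume independent visits and treat equal quotas across locations and provider types as one simple random sample. The clustered figures rest on an assumed correlation. On any of these assumptions, the comparison of provinces within the private sector can only be descriptive.

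**What to change.** - **Sections 3.1 and 8.1:** describe the study as a quantitative cross-sectional survey using structured, disguised observation, and delete the saturation sentence.
- **Sections 5.1 and 8.1:** reconcile the practitioner numbers (five and five, or nine and nine). State the resulting total as a fixed target that is not extended on the basis of results. Keep the provision in section 4.1 for an additional site when numbers fall short, and align its 160 caregivers with the reconciled total.
- **Section 8.1:** state the expected precision overall, per location, and for public and private providers within a location. Give the assumptions (95%, p = 0.5, independent visits) and label it best case as regards clustering. With 160 the half-widths are 7.7, 17.3, 20.4 and 32.7 points; if the number changes, recompute them. Say that two data collectors per location and reuse of caregivers would widen them. This discloses the precision of a quota chosen on other grounds; if the sponsor has a target precision, it should be stated.
- **Section 8.2:** report province and sector percentages with confidence intervals that allow for clustering by data collector and for repeated use of a caregiver, and name the method. The eCRF already records the data collector and the subject ID.
- **Section 2.1.2:** word the secondary objective as descriptive.

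The cost is protocol wording and a modest addition to the analysis; no observations are added. The downside is that the stated precision for province-by-sector results will look unfavourable.

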8.2 PROPOSED ANALYSES

Behavioural coding will be employed to prepare the data for analysis. This means that a predetermined code will be given to each variable against each category of observations (History, examination, diagnosis and treatment). Each variable will be answered as "Y" meaning yes, the task was accomplished and "N" meaning no, the task was not accomplished (section 6.1). Additionally, the responses will be labelled as correct, partially correct and incorrect for history taking and examination. If on history taking, the healthcare provider asks questions on all variables, then the responses will be labelled as correct and if any one variable is missed then the response is indicated as partially correct and in case less than 50% of the variables are asked about, then the responses will be labelled as incorrect. The same labels will be specified for the examination. In case of diagnosis and treatment, the labels will be specified as correct and incorrect only as there is no partially correct diagnosis and treatment regimens. The overall frequencies and percentages of these responses will be calculated and cross tabulated across the provinces.

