2.2 ENDPOINTS

2.2.1 Primary Endpoint

1. Correct history taking of case of pneumonia
2. Correct examination of case of pneumonia
3. Correct diagnosis of case of pneumonia
4. Correct treatment of case of pneumonia

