ANNEX C- OBSERVATION TOOL

CLINICAL OBSERVATIONS (were the following parameters followed)	
1. History taking	Y/N
Cough	
Fast breathing	
Laboured breathing	
Fever	
Immunization	
Breastfeeding history	
Overcrowding	
Parental smoking/Household member smoking	
Air pollution (indoor cooking stove)	
Nutritional history	
Hygienic practices	
Family history of HIV	
2. Examination (Did the healthcare provider make the following necessary examinations apart from others)	
Temperature	
Respiratory rate counting for 1 minute	
Pallor	
Skin rash	
Examine lower chest in drawing	
Auscultate for wheeze or crepts	
3. Diagnosis (Did the healthcare provider make the correct diagnosis based on WHO guidelines)	
Cough with no fast breathing/chest in drawing: No pneumonia	
With fast breathing and/or chest in drawing : Pneumonia	
Pneumonia with any danger signs : Severe Pneumonia	
4. Management (Did the healthcare provider manage the case per the guidelines)	

No Pneumonia: Symptomatic treatment	
Pneumonia: Oral amoxicillin 40mg/kg/dose twice daily for three days	
Severe Pneumonia: For LHWs: First dose of oral antibiotic (amoxicillin) and referral to health facility and For BHUs: First dose of oral antibiotic (amoxicillin) and referral to rural health centre or tertiary care hospital For health facilities (public and private) : Parenteral ampicillin 50mg/kg IV 6 hourly for five days along with gentamicin 7.5mg/kg/ IM or IV for five days.	

SCORE: (Count the total number of Y and enter the value in the table below)

ACTIVITY OBSERVED	“ Y” SCORED	TOTAL
History Taking		12
Examination		6
Diagnosis		1
Management		1

OBSERVATION RESULT*:

ACTIVITY OBSERVED	SELECT THE APPROPRIATE RESPONSE
History Taking	Correct/partially correct/ incorrect
Examination	Correct/partially correct/ incorrect
Diagnosis	Correct/ Incorrect
Management	Correct/ Incorrect

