***RESULT CRITERIA:**

For history taking:

Correct: Score of 12

Partially correct: Score of <12 but >6

Incorrect: Score of <6

For Examination:

Correct: Score of 6

Partially correct: Score of <6 but >3

Incorrect: Score of <3

For Diagnosis:

Correct: 1

Incorrect: 0

For Management:

Correct: 1

Incorrect: 0

Any other pertinent information:

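### The history and examination endpoints require every checklist item, and section 8.2 plans no summary of the 0-12 and 0-6 scores that Annex C already records, which loses information on differences between provinces and levels of care

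*Combined protocol and SAP*

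**What the plan says.** Section 2.2.1 lists "Correct history taking of case of pneumonia" and "Correct examination of case of pneumonia" among the four primary endpoints and gives no threshold for either. Section 8.2 supplies the scale: "the responses will be labelled as correct, partially correct and incorrect for history taking and examination". The top label needs every item, and "if any one variable is missed then the response is indicated as partially correct". The lowest label applies below half: "in case less than 50% of the variables are asked about, then the responses will be labelled as incorrect".

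The Annex C result criteria repeat three levels, with the top history level given as "Correct: Score of 12". The top examination level is a score of 6.

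Annex C also has the raw score recorded, out of 12 for history and out of 6 for examination: "Count the total number of Y and enter the value in the table below". Section 8.2 codes each item Y or N, but the only summaries it plans are frequencies and percentages of the responses, overall and by province. It plans no mean, median or interval for the score, and no table by level of care or sector.

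The primary objectives (2.1.1) concern practice at three levels of care and in the private sector. Differences between provinces, in both sectors, are the secondary objective (2.1.2).

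**The concern.** The middle history label covers every score from 6 to 11 under section 8.2. Two provinces can differ clearly in how many items providers cover and still put most visits into that one category. The score that would show the difference is on the form but has no place in the analysis.

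The top category may also be sparse for history. Section 6.1 marks eight of the 12 history items as predisposing factors, and these do not enter its diagnosis rule. Section 7, however, explains that "essential care refers to the questions providers must ask the caregiver and examinations provider must conduct to accomplish correct diagnosis". A provider who asks about all four presenting complaints but omits overcrowding or family history of HIV misses the named endpoint. That strictness may be a deliberate choice. It is still a reason not to rely on the label alone.

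With 32 visits per location, and 4 to 9 per provider type within each, the study has little information to spare.

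**Working it through.** **Inputs from the documents.** Section 8.1 gives 6 + 4 + 4 + 9 + 9 = 32 visits per location and 32 × 5 = 160 in total, which reproduces the stated minimum. There are 12 history and 6 examination items. I used the section 8.2 cut-offs, so incorrect is 0-5 for history and 0-2 for examination. The Annex C criteria give no label to a score of exactly 6 or 3; section 8.2 makes both partially correct.

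**Assumptions.** The documents state no item rates, alpha or power. I assume a common item rate *p*, two-sided 5% tests, and items that are either independent or beta-binomial with within-visit correlation ρ.

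**1. Share labelled correct, independent items: *p* to the power *k*.**

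| *p* | History (*k* = 12) | Examination (*k* = 6) |
|---|---|---|
| 0.5 | 0.02% | 1.6% |
| 0.7 | 1.4% | 12% |
| 0.8 | 6.9% | 26% |
| 0.9 | 28% | 53% |

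At *p* = 0.7 the chance of no correct history in 32 visits is (1 − 0.0138)^32 = 0.64. Correlation raises the share: at ρ = 0.1, correct history is 6.9% at *p* = 0.7 and 18% at 0.8, and the chance of none in 32 visits at 0.7 falls to about 10%.

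**2. Where the visits fall.** With independent items, partially correct history holds 95% of visits at *p* = 0.7 and 93% at 0.8. The two tables would look almost the same.

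**3. Power of the score in closed form, 0.7 v 0.8, 32 v 32.** The difference in means is 0.1*k*. Its standard error is √{*k*(0.21 + 0.16)[1 + (*k* − 1)ρ]/32}.

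- History, ρ = 0: 1.2/√(4.44/32) = 1.2/0.372 = 3.22, so power is Φ(3.22 − 1.96) ≈ 0.90.
- History, ρ = 0.1: the variance is multiplied by 2.1, so 1.2/0.540 = 2.22 and power is ≈ 0.60.
- Examination, ρ = 0: 0.6/√(2.22/32) = 0.6/0.263 = 2.28, so power is ≈ 0.62.
- Examination, ρ = 0.1: the variance is multiplied by 1.5, so 0.6/0.323 = 1.86 and power is ≈ 0.46.

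**4. Score against the planned three-level label, by simulation** (Welch t on the score, Mann-Whitney on the label; repeat runs agree within about two percentage points).

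| 0.7 v 0.8, 32 v 32 | Score | Three-level label |
|---|---|---|
| History, ρ = 0 | 87% | 26% |
| History, ρ = 0.1 | 59% | 38% |
| History, ρ = 0.2 | 43% | 36% |
| Examination, ρ = 0 | 62% | 41% |
| Examination, ρ = 0.1 | 46% | 37% |
| Examination, ρ = 0.2 | 37% | 33% |

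**5. Larger differences.** With item rates 0.15 apart (from 0.40 v 0.55 to 0.60 v 0.75), 32 v 32, history power is 98-99% for the score and 68-94% for the label at ρ = 0, and 64-68% against 50-57% at ρ = 0.2. For 30 v 45 visits (all LHWs against one practitioner group) it is 99-100% against 75-95%, and 69-73% against 56-63%.

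The score had more power than the label in every scenario. The simulations ignore clustering by data collector and by shared caregiver.

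**The case against.** A reader might infer that the labels are all-or-nothing, that the share correct will be near zero everywhere, and that the endpoints therefore cannot separate provinces or levels. The documents do not support this. The scale has three levels with a 50% cut, and all three are tabulated. Comparing the score with the correct share alone would give a far larger contrast (about 1% power for history with independent items at 0.7 v 0.8), but that share is not the only planned summary. With item rates 0.15 apart, the label keeps about 69-96% of the score's power for history and about 75-90% for examination at 32 v 32. A near-empty top category depends on assumed item rates: it is plausible for history at about 0.7 or below, much milder for examination, and absent for both at 0.9.

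It can also be said that the study calls itself qualitative, plans no tests, and could validly report that few providers complete the checklist. That is fair, and power serves here only as a measure of information. The study still sets out to compare provinces, and a descriptive report needs summaries that show differences where they exist.

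Finally, the responses that section 8.2 tabulates may include the item-level Y/N codes as well as the labels; the wording allows either reading. Nothing recorded is destroyed. Neither reading provides a summary of the total scores.

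**Conclusion.** The point holds as a loss of information. The named endpoints need 12 of 12 and 6 of 6, the planned analysis uses a three-level label, and the recorded scores have no planned summary. At assumed item rates of 0.7 v 0.8 with 32 visits per group, the label takes history power from about 87% to 26% with independent items and from 59% to 38% at correlation 0.1. For examination it falls from about 62% to 41% and from 46% to 37%. By correlation 0.2 the gap is 7 points for history (43% v 36%) and 4 for examination (37% v 33%). These sizes depend on the assumed rates, correlation and 5% level; the direction was the same in every scenario.

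For comparisons between levels of care there is a more direct gap: section 8.2 tabulates by province only, although the primary objectives are about levels and the private sector.

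**What to change.** Keep the three labels as they are. In section 8.2, add:

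- the mean 0-12 history score and mean 0-6 examination score, each with a 95% interval;
- the percentage Y for each item, stated explicitly so that the present ambiguity is removed;
- these summaries and the label table by province, by sector and by level of care.

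The cost is analysis wording only. The item responses, totals, place of visit and location are already on the forms, so no new data, visits or form fields are needed.
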